6.2.1.3 SEVERITY

When evaluating AEs, the Investigator must determine the severity of symptoms using the following guidelines:

- Mild: Subject awareness of a sign or symptom that is easily tolerated, requires no treatment, and does not interfere with the subject's daily activities
- Moderate: Subject awareness of a sign or symptom which may be a low level of concern to the subject and may interfere with daily activities, but can be relieved by simple therapeutic care
- Severe: A sign or symptom that interrupts the subject's daily activity and requires systemic therapy or other treatment

6.2.1.4 RELATIONSHIP (CAUSALITY) TO STUDY DEVICE OR STUDY PROTOCOL

When evaluating AEs, the Investigator must evaluate the relationship of the event to the study device and study protocol, using the following guidelines:

- Not Related: AEs which are clearly and incontrovertibly due to causes other than the study device or study protocol (e.g. concomitant disease, etc)
- Related: AEs which are felt with a reasonable degree of certainty to be related to the study device or study protocol
- Unknown: Adverse events for which a connection with the study device or study protocol cannot be ruled out with certainty, or not enough information is available to assess the relationship

6.2.1.5 OUTCOME

The clinical outcome of an AE will be categorized as follows:

- Resolved without sequelae
- Resolved with sequelae (specify)
- Ongoing (i.e. continuing at time of study discontinuation)
- Death

6.2.1.6 TREATMENT OR ACTION TAKEN

Treatment or Action Taken will be categorized as follows:

- None
- Medical Intervention (specify on Concomitant Medication Source and eCRF)
- Surgical Intervention (specify on Concomitant Procedure Source and eCRF)
- Other (specify)

6.3 REPORTING

6.3.1 ON-SITE EXPEDITED REPORTING

The Investigator is obligated to report the following to the Sponsor within 24 hours of becoming aware of the event to ensure the safety of all participants in the study and to meet regulatory reporting requirements:

- All SAEs, regardless of relationship to study device or study protocol utilizing the SAE/ADE Report Form
- All AEs determined to be related to the study device (ADEs or UADEs) utilizing the SAE/ADE Report Form
- All HMTIOL expantants (consult Medical Monitoring on Protocol Contacts page prior to expantant, if possible)
- All Device Deficiencies (DD) utilizing the DD Report Form

Refer to the Protocol Contacts page for appropriate Sponsor contact to report the above events.

NOTE: Any explanted HMTIOL devices, exchanged HMTIOL optics, or any components of the HMTIOL System presenting a deficiency or malfunction are to be retained by the site until collected by the Sponsor. Under no circumstances are they to be destroyed or otherwise discarded.

When reporting these events to the Sponsor, the site should forward any supporting documents along with the appropriate reporting form and complete the corresponding eCRF, if applicable. Sites must also report applicable events to the reviewing IRB/EC per established reporting procedures.

CLARV STA MED CAL

PROTOCOL CP 00004 REV 01

6.3.2 OFF-SITE SAE REPORTING

As a multicenter clinical trial, the Investigators may receive "off-site" reports (e.g. an SAE Report). These are Sponsor reports of SAEs which occurred at other sites for the same trial, or different trials using the same test article, that met the criteria for reporting. These should be reported to the reviewing IRB per the established reporting procedures.

6.3.3 REPORTING OF COMPLAINTS FOR ANCILLARY MARKETED PRODUCTS

Any complaints, malfunctions or similar events related to ancillary marketed products used in this study should be reported by the Investigators in accordance with the reference information provided on the associated commercial packaging.

6.3.4 ADVERSE EVENTS AND SERIOUS ADVERSE EVENTS AT SUBJECT EXIT

Ongoing SAEs and ADEs will be followed until resolution or no further change in the conditions expected. Non-serious AEs that are ongoing at study exit versus or upon discontinuation from the study will be followed per the Investigator's standard of care. Documentation in the eCRF of these follow-ups not required although subject care should continue as appropriate.

6.4 SAFETY MONITORING AND REVIEW

All reported AEs will be reviewed on a weekly basis and assessed for trending and causality to study device or procedure. ADEs, UADEs, DDs, and SAEs will be reviewed upon receipt of expedited reporting (Section 6.3.1). Any unexpected trends or events will necessitate careful review and assessment of any change in the risks associated with participation on or study discontinuation.

If an event occurs affecting a subject's risk of participation, Off-Site Reporting (Section 6.3.2) will be utilized to update sites and the IRB(s) / EC(s) if the safety profile of the event provides for the continuation of the study, informed Consent Forms will be revised as necessary to ensure subjects' consent to continue participation given the known revised risks.

As outlined in Section 4.7.1, the Sponsor reserves the right to discontinue enrollment at any time.

7.0 STUDY OUTCOMES**7.1 SAFETY OUTCOMES**

Safety will be evaluated by assessing the following:

- Preservation of BCDVA
- Rate of device-related SSI's other than optical exchange and rotational adjustment of the HMTIOL
- AE rates
- Device deficiencies

7.2 PERFORMANCE OUTCOMES

- Calculation of Standard error of the mean, sensitivity, power, A-constant for refinement
- 1 and 3 months MRCYL for eyes implanted with HMTIOL
- 1 and 3 months MRCYL prediction error for eyes implanted with HMTIOL
- 1 and 3 months MRCYL prediction error for eyes implanted with HMTIOL per vector analyses

CLARV STA MED CAL

PROTOCOL CP 00004 REV 01

- 1 and 3 months SEQ prediction error
- UCDVA by study visit
 - Percent of eyes that achieve
 - 20/20 or better
 - 20/25 or better
 - 20/32 or better
 - 20/40 or better
 - Worse than 20/40
- BCDVA by study visit
 - Percent of eyes that achieve
 - 20/20 or better
 - 20/25 or better
 - 20/32 or better
 - 20/40 or better
 - Worse than 20/40
- IOL meridian measurement on the day of surgery
- Rotation of IOL meridian at 1 day, 1 week, 1 and 3 months
 - Percent of eyes with rotation ≤ 5
 - Percent of eyes with rotation < 10
 - Percent of eyes with rotation < 20
 - Percent of eyes with rotation < 30
 - Absolute value of rotation
 - [REDACTED]
- Reduction in cylinder power of the eye implanted with HMTIOL (absolute preoperative magnitude of corneal cylinder (K) minus the absolute postoperative magnitude of MRCYL at the corneal plane)
- Percentage reduction in cylinder power of the eye implanted with HMTIOL (absolute preoperative magnitude of corneal cylinder (K) minus the absolute postoperative magnitude of MRCYL at the corneal plane, expressed as a percentage of the absolute preoperative magnitude of total corneal cylinder (K)).

[REDACTED]

[REDACTED]

8.0 STATISTICAL METHODS

This is a study to evaluate the safety and performance of HMTIOL in subjects undergoing cataract surgery. In general, the analyses will be provided based on available data. The mean, standard deviation, minimum, and maximum will be prepared for the continuous clinical parameters, and counts and percentages will be presented for the categorical outcomes.

8.1 SAMPLE SIZE CALCULATION

The sample size of this study is based on refinement of A-constant (lens power constant). To reduce bias due to surgical technique, unusual eyes and differences in equipment (A scan, keratometer, etc.) data will be obtained from a sufficient number of eyes such that the standard error of the mean in lens power constant is less than ±0.10mm (approximately ±0.2D). A minimum of 20 to 30 eyes from each surgeon should be adequate to achieve the tolerance. Each included subject should have a post-operative uncorrected visual acuity better than 20/40 to avoid inaccuracies in refraction.

This is a feasibility study and no hypothesis testing will be performed.

8.2 ANALYSES POPULATIONS

Subjects that are screened but disqualified based on the preoperative and intra-operative eligibility criteria will be excluded from the safety and performance data analyses. However, the reasons for the screen failure will be summarized. The analyses populations are defined below.

8.2.1 SAFETY POPULATION

The **Safety Population** includes eyes with attempted study lens implantation, (successful or aborted after contact with the eye). The intraoperative and postoperative AEs and DDs will be summarized based on the safety population.

8.2.2 IMPLANTED-EYE POPULATION

The **Implanted-Eye** Population consists of eyes with successful HMTIOL implantation. Since it is important to evaluate HMTIOL's effect on a study eyes, slit lamp examination, intraoperative pressure (IOP), and dilated fundus examination (DFE) will be based on the implanted-eye population.

Additionally, the UCDVA, BCDVA, prediction error, and meridional rotation will be evaluated based on the implanted-eye population.

8.2.3 PER PROTOCOL POPULATION

The **Per Protocol** (PP) Population contains eyes with successful HMTIOL implantations during surgeries and do not have a major protocol deviation (such as improperly enrolled in the study or lens power calculation errors) and will be considered the primary population for the analysis of performance outcomes. The performance outcomes (UCDVA, BCDVA, and prediction error) will also be evaluated based on the per protocol population.

The protocol deviations will be categorized prior to the analysis.

[REDACTED]

- [REDACTED]
- [REDACTED]
- [REDACTED]
- [REDACTED]
- [REDACTED]
- [REDACTED]
- [REDACTED]

- [REDACTED]
- [REDACTED]

[REDACTED]

8.3 STATISTICAL METHODS

The data analyses will be based on the analysis populations described above. No imputation for missing data will be performed. The demographic data will be summarized based on study subjects.

For continuous outcomes, mean, standard deviation, median, minimum, and maximum will be provided. For categorical outcomes, the counts and percentages of eyes with each category level of outcomes will be summarized.

8.3.1 SAFETY OUTCOMES

8.3.1.1 ADVERSE EVENTS AND DEVICE DEFICIENCIES

Adverse events and device deficiencies will be summarized at each study visit based on the safety population. The number and percentage of eyes reported with the 3-month cumulative and persistent adverse events will be calculated. [REDACTED]

[REDACTED]

[REDACTED]

[REDACTED]

[REDACTED]

8.3.2 PERFORMANCE OUTCOMES

The performance outcomes will be analyzed based on the Impacted-eye Population and PP Population. The BCDVA will also be summarized based on the Best-case population as suggested by ISO.

8.3.2.1 BCDVA

[REDACTED]

[REDACTED]

[REDACTED]

[REDACTED] the number and percentage of eyes reaching BCDVA 20/20 or better, 20/25 or better, 20/32 or better, 20/40 or better, and worse than 20/40 at each visit will be prepared.

[REDACTED]

CLARV STA MED CAL

PROTOCOL CP 00004 REV 01

8.3.2.2 UCDVA

The proportion of eyes with UCDVA of 20/20 or better, 20/25 or better, 20/32 or better, 20/40 or better, and worse than 20/40 at each visit will be summarized at the preoperative and every postoperative visits.

8.3.2.3 PREDICTION ERROR (PE)

The MRSE prediction error will be calculated at 3 months for each implanted eye as follows:

MRSE PE = Postoperative MRSE adjusted to 6 meters – MRSE TRRE (target residual refractive error)

The MRCYL prediction error will be calculated at 3 months for eyes implanted with HMTIOL as follows:

MRCYL PE = Postoperative MRCYL adjusted to 6 meters – MRCYL TRRE (target residual refractive error)

The MRCYL PE will also be calculated based on the vector analysis approach for eyes implanted with the HMTIOL.

[Redacted text block]

8.3.2.4 MISALIGNMENT OF IOL MERIDIAN

The final rotational meridian of the IOL will be compared to the planned position. The absolute value of rotation will be described by mean, median, and maximum values.

[Redacted text block]

8.3.2.5 ROTATION OF IOL MERIDIAN

The rotation of IOL meridian will be calculated for each eye from Day 0 to every postoperative visit. The descriptive statistics for continuous variables will be used to summarize the rotation angle at each visit. The absolute value of rotation will be described by mean, median, and maximum values.

The number and percentage of eyes with rotation ≤ 5 , < 10 , < 20 , and < 30 will be calculated at each visit.

[Redacted text block]

8.3.2.6 REDUCTION IN CYLINDER POWER

CLARV STA MED CAL

PROTOCOL CP 00004 REV 01

The reduction in cylinder power will be calculated for each eye implanted with the HMTIOL as follows:

$$\text{Cylinder Power Reduction} = \text{absolute value of preoperative magnitude of corneal cylinder (K)} - \text{absolute postoperative magnitude of MRCYL at the corneal plane.}$$

The percent reduction in cylinder power will be calculated for eyes with non-zero preoperative corneal cylinder as follows:

$$\text{Cylinder Power \% Reduction} = \text{Cylinder Power Reduction} / \text{absolute value of preoperative magnitude of corneal cylinder (K)} \times 100.$$

The descriptive statistics for continuous variables will be used to summarize these outcomes at each visit. [REDACTED]

The vector analyses (Eyde man¹¹) based on the cylinder power and axes will be performed. [REDACTED]

9.0 DATA MANAGEMENT

9.1 DATA QUALITY ASSURANCE

All requested information must be entered on the eCRF and confirmed through source documentation. If an item is not available or not applicable, this fact should be clearly indicated.

Data will be entered into a computer database developed specifically for this trial. During the course of the trial, queries will be generated for data points that are potentially erroneous and require appropriate clarification or correction.

9.1.1 DATA MONITORING

Periodic monitoring (either remote and/or on-site) will take place to ensure data integrity. Study monitoring involves the following elements:

Clarvista personnel, or designee, may meet with investigators prior to the initiation of the study in order to review the adequacy of the subject population, facilities, and equipment with respect to the needs of the study, and to familiarize the investigator and support staff with the study protocol.

Clarvista personnel, or designee, may meet with the investigators at the time enrollment is initiated in order to ensure that subjects are being properly selected, that the methods described in the study protocol are thoroughly understood by the investigator, and that study data are being correctly recorded.

CLARV STA MED CAL

PROTOCOL CP 00004 REV 01

CarV sta personne , or des gnee, may v s t the c n ca s te at any t me dur ng the course of the study to rev ew and/or co ect comp eted case report forms. Add t ona y, te ephone consu tat on w occur as necessary dur ng the course of the study to ensure the proper progress and documentat on of the study f nd gns.

The study data w be carefu y protected, and mask ng ut zed to the extent poss b e, n order to prevent b as.

9.2 RECORD RETENTION

The nvest gator sha ma nta n a subject records for wh chever of the fo ow ng per ods s shorter:

- A per od of two years after the date on wh ch FDA approves the market ng of the dev ce
- A per od of f ve years after the date on wh ch the resu ts of the study are subm tted to the FDA n support of the market ng of the dev ce

OR

- A per od equa to the m n mum requ red by the reg ona author ty.

The Invest gator / S te must contact CarV sta as prov ded n the Protoco Contacts page pr or to d scard ng or d spos ng of any study re ated supp es or documents. The Sponsor reta ns the r ght to have a study documents sh pped (at Sponsor's expense) for arch va purposes, as an a ternat ve to d sposa .

APPENDIX A – TABLE 1: SCHEDULE OF ASSESSMENTS

Procedure/Assessment	Pre-Op Visit ¹ Day -90 to -0	Op Visit		Form 3 1 Day Visit (Day 1-2 from Day 0 of the eye)	Form 4 1 Wk Visit (Day 7-14 from Day 0 of the eye)	Form 5 1 Mo Visit (Day 30-60 from Day 0 of the eye)	Form 6 3 Mo Visit (Day 80-100 from Day 0 of the eye)
		First Eye Day 0	Second Eye (if enrolled) Day 0 (+3-30 Days from the first eye surgery)				
Informed Consent	X						
Demographics	X						
Med/Ophthalmic History	X	X	X				
Eligibility ²	X	X	X	X	X	X	X
UCDVA ³	X						
Auto and Manifest Refraction	X				X	X	X
BCDVA	X				X	X	X
Keratometry ⁴	X					X	X
Axial Length	X						
Anterior Chamber Depth	X						
IOL/Toric Power Calculation ⁵	X						
Slit Lamp Examination	X			X	X	X	X
IOP	X			X	X	X	X
Pupil Size	X	X	X				
Surgery / IOL implantation		X	X				
IOL Rotational Stability ⁶		X	X	X	X	X	X
[REDACTED]							X
Dilated Fundus Exam	X						

¹ All testing to be conducted on both eyes

[figure not shown]
² Will include pregnancy test if applicable

³ If UCDVA is < 20/40, perform Pinhole (PH) vision

⁴ Measurements via biometry will be utilized for both calculations and data capture

⁵ To be reviewed and approved by the Sponsor

⁶ Rotational stability as assessed by Reading Center

Alcon - Business Use Only

Document: TDOC-0055987

Status: Effective

Effective Date: 24-Apr-2019

Version: 1.0; CURRENT; Most-Recent; Effective

1 TITLE PAGE

Protocol Number:	ClarVista CP-00004 / NCT03050697
Medical Specialty:	Surgical
Project Name /Number:	NA
Sponsor Name & Address:	CLARVISTA MEDICAL, INCORPORATED [name] [name] [contact] [contact]
Test Article(s) / Product(s):	ClarVista HARMONT® Modular Toric Intraocular Lens System

SAP CP-00004

ClarVista Medical, Inc.

Statistical Analysis Plan for Protocol CP-00004

A Prospective, Multi-Center Study to Evaluate the Safety and Performance of the ClarVista HARMONI® Modular Toric Intraocular Lens System for the Treatment of Pre-Existing Corneal Astigmatism and Aphakia Following Cataract Surgery

Sponsor

ClarVista Medical, Incorporated
[name]
[name]
[contact]
[contact]

Original Version Date

29 June 2017

SAP CP-00004

ClarVista Medical, Inc.

Table of Contents

1. Purpose	3
2. Scope	3
3. Software	3
4. Design and Objectives	3
5. Statistical Analyses	3
6. Sample Size	6
7. Analysis Populations	7
█ [REDACTED]	
█ [REDACTED]	
10. Interim Analyses	8
11. Deviations from the Statistical Analysis Plan	8
12. References	8

SAP CP-00004

ClarVista Medical, Inc.

1. Purpose

This Statistical Analysis Plan documents and describes the planned analyses for study CP-00004. This is a study to evaluate the safety and performance of the HARMONI Modular Toric Intraocular Lens System (HMTIOL) in patients with pre-existing corneal astigmatism. Specifically, the intent is

- To evaluate the refractive outcomes including astigmatism correction with HMTIOL in primary cataract surgery
- To evaluate axial and rotational stability of the HMTIOL

Given these goals, there are no formal hypothesis tests for safety or effectiveness. All results will be purely descriptive.

2. Scope

This document is based on the Investigational Plan CP-00004. [REDACTED]

As the multi-center study described in the Investigational Plan was not actually implemented, analyses described here supersede those described in the Investigational Plan.

3. Software

Statistical analyses will be performed with SAS System Software version 9.4 or above (SAS Institute, Cary, N.C.), R version 3.3 or above (R Core Team, <http://www.R-project.org>), or other validated statistical software package.

4. Design and Objectives

CP-00004 was designed as a prospective, multi-center, cohort study. However only one center actually enrolled patients in the trial.

All patients in this study require cataract extraction and implantation with intraocular lenses. Patients have pre-existing corneal astigmatism in the study eye(s). The magnitude of astigmatism is within the range of available toric powers: 1.50, 2.25 and 3.00 D at the IOL plane, after adjusting for Surgically Induced Astigmatism.

One or both eyes of each subject will undergo cataract surgery and be implanted with the HMTIOL. Eyes with corneal astigmatism that is within the dioptric range of the toric IOL will be implanted.

All eyes will be followed for 1 Day, 1 Week, 1 Month, and 3 Months following cataract extraction.

5. Statistical Analyses

5.1. General Statistical Methods

For continuous measures, descriptive summary statistics will include the number of observations, mean, standard deviation, median, minimum, maximum, as well as the number of eyes with results not reported.

[REDACTED] Continuous measures may also be dichotomized or otherwise split into clinically meaningful categories and additionally analyzed as categorical measures.

For categorical measures, the percentage and number of cases for each condition (e.g., 20/40 or better) will be reported. The number of eyes without results will be omitted from the numerator and denominator of such calculations (i.e. no imputation will be performed).

SAP CP-00004

ClarVista Medical, Inc.

5.2. Baseline Data

Data on enrollment, demographics (gender, race, age, implanted eye), and baseline characteristics (IOL Power, pre-operative MRSE, target MRSE, keratometric cylinder, axial length) will be summarized with descriptive statistics.

5.3. Accountability

Accountability will be based on eyes (not subjects). The number and percentage of eyes available for analysis at each time point will be presented.

5.4. Safety Endpoints

- Preservation of BCDVA
- Adverse Events as outlined in ISO 11979-7:2014 Annex B
- Rate of device-related Secondary Surgical Interventions (SSIs) other than optic exchange or rotational adjustment of the HMTIOL
- Device deficiencies

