1. Post-operative correction of residual spherical refractive error – Based on existing performance of conventional cataract surgery, researchers have concluded that refractive outcomes in normal eyes should be within 0.5D for 45% and within 1D for 85% of cataract cases⁵. This theoretical performance goal is substantially short of the real-world outcomes seen with corneal refractive surgery and which cataract patients and surgeons increasingly demand. As a consequence, secondary procedures to optimize visual outcomes following cataract surgery can be as high as 16% in some practices, particularly for premium lens patients².

Modular IOL technology is intended to directly improve refractive outcomes without the inherent risk of a full lens exchange or resorting to the use of a corneal refractive laser. With the HARMONI™ designed spherical optic component is intended to allow exchange for a different power optic or adjusted to a given visual axis without extensive manipulation of the delicate capsular bag, thereby avoiding the potential for intraocular (e.g., capsular and endothelial) trauma that is seen with traditional IOL exchanges.

2. Post-operative correction of rotational decentered or off-axis toric lenses – For every 1 degree a toric IOL axis is off from the true postoperative axis of astigmatism, there will be a 3.3% loss of toric correction. Study data supporting a recent approval of a toric IOL (P930014/S045) showed that 6.7% of eyes underwent a secondary surgical intervention (SSI) in the form of IOL repositioning to resolve RRE. The HARMONI™ modular technology can be used to improve outcomes in patients where the toric lens has been decentered to an unintended position during the post-operative period. The HARMONI™ optic allows for adjustment to a given visual axis without manipulation of the base component thereby avoiding the potential for capsular trauma that is seen when toric IOLs are manipulated in the post-operative period.

The Clarvsta Harmon™ Monofocal (non-toric) Modular IOL System has been available since 2015. A toric version, the Clarvsta Harmon™ Toric Modular IOL System (HMTIOL), has been recently CE-approved.

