4.8.2 CONCOMITANT PROCEDURES

A concomitant procedure is any invasive or non-invasive ocular or per-ocular procedure that takes place during study participation and will be captured in both the Concomitant Procedure Source Document and eCRF. The following are examples of two such procedures:

- Any PO surgical adjustments (i.e. cornea refractive surgery, lens exchange, lens rotation, etc.)
- Neodymium: Yttrium-aluminum-garnet (Nd:YAG) procedure to treat Posterior Capsule Opacification (PCO), if necessary. This will be listed as "Nd:YAG Capsulotomy."

Note: Any Nd:YAG capsulotomy procedures prior to exit will be performed only in response to spontaneous subject complaints (i.e. not solicited by study personnel) of reduced Visual Acuity (VA) or glare that affects functional vision, which is associated with PCO or striae, and captured on the eCRF in SLE findings.

CLARV STA MED CAL

PROTOCOL CP 00004 REV 01

An AE s to be reported and/or recorded as appropriate (see Section 6.0). Any procedure reported in the Concomitant Procedure eCRF must have a corresponding Indication listed in either the Ocular History or AE eCRF (Only exception: PCO – See Section 6.1 for further details).

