6.1 DEFINITIONS

6.1.1 ADVERSE EVENT (AE)

An AE is any untoward medical event in a subject that does not necessarily have a causal relationship to the study device or protocol. AEs include Adverse Device Effects (ADEs). Conditions or diseases that are pre-existing and/or chronic but stable should not be recorded on AE pages of the eCRF. Similarly, changes in a pre-existing and/or chronic condition of disease that are consistent with natural disease progression are NOT adverse events and also should not be recorded on the AE pages of the eCRF.

Refer to Section 6.3.1 for instructions regarding events that require expedited reporting to the Sponsor and IRB/EC.

CLARV STA MED CAL

PROTOCOL CP 00004 REV 01

Experience with cataract surgery and the important role of IOLs has shown that some conditions can be considered normal or expected events following these procedures. The following may be considered normal or expected events after cataract surgery and only need to be reported as AEs as specified here:

- Irritation (redness) – if treated longer than standard post-operative regimen or if it recurred after complete resolution
- Persistent Cornea Stroma Edema (if present at 1 Month)
- Increased IOP on any follow-up medical/surgical intervention(s) required (i.e. medication, paracentesis manipulation)
- BCDVA decrease of 10 or more letters (2 lines) from any previous visit not secondary to any underlying condition present at time of enrollment
- Any expected post-operative ocular event requiring a change in standard postoperative medication regimen

Note: PCO is not to be reported as an AE, as per ISO 11979-7:2014.

Note: The HMTIOL is designed for safety and ease of optic exchange and rotational adjustment post-primary cataract surgery. Optic exchange and optic rotation to refine refractive outcomes are not to be reported as AE's.

Particular attention should be paid to ensure timely and accurate reporting of any of the following cataract surgery related events:

- Endophthalmitis
- Capsular injury
- Vitreous loss
- Macular edema
- Retinal detachment
- Lens dislocation
- Moderate to severe cornea edema
- Pupillary block / angle closure
- Hypopyon or hyphema

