5.5. Safety analyses

All endpoints listed above will be summarized by study visit and cohort as described in section 5.1. There are no formal hypothesis tests for safety.

The number and percentage of eyes reaching BCDVA 20/40 or better, and worse than 20/40 at each visit will be prepared.

Rates for adverse events specified in ISO 11979-7:2014 Annex B for posterior chamber IOLs will be summarized at each visit.

Rates of device-related SSIs and device deficiencies will be summarized as described in 5.1 above.

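### The SSI safety rate excludes every optic exchange and rotational adjustment whatever the reason, and no visible output counts them, so 0/17 would not mean that no lens was re-operated

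*SAP*

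**What the plan says.** **Endpoint.** SAP 5.4 names the safety endpoint as the "Rate of device-related Secondary Surgical Interventions (SSIs) other than optic exchange or rotational adjustment of the HMTIOL". Protocol 7.1 has the same exclusion: "Rate of device-related SSI's other than optical exchange and rotational adjustment of the HMTIOL". The protocol synopsis agrees. None of the three attaches a condition on the reason for the procedure.

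**Planned outputs.** SAP 5.5 states: "Rates of device-related SSIs and device deficiencies will be summarized as described in 5.1 above". On adverse events it states: "Rates for adverse events specified in ISO 11979-7:2014 Annex B for posterior chamber IOLs will be summarized at each visit". SAP section 2 says that its analyses replace those in the protocol.

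**AE exemption.** Protocol 6.1.1 gives a design reason (the lens is made so that its optic can be exchanged or turned after surgery) and then a rule: "Optic exchange and optic rotation to refine refractive outcomes are not to be reported as AE's".

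**Recording.** Protocol 4.8.2 gives as an example of a concomitant procedure "Any PO surgical adjustments (i.e. cornea refractive surgery, lens exchange, lens rotation, etc". It adds that any procedure so logged "must have a corresponding Indication listed in either the Ocular History or AE eCRF (Only exception: PCO".

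**Background.** Protocol 1.0 reports, for a different toric lens, that "6.7% of eyes underwent a secondary surgical intervention (SSI) in the form of IOL repositioning to resolve RRE". SAP section 6 sets the sample at 17 enrolled and treated eyes and plans no hypothesis test.

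**The concern.** Two rules for the same procedures use different boundaries. The SSI exclusion goes by procedure; the AE exemption goes by purpose. Optic exchanges or rotations done for a device reason, such as a damaged or dislocated optic, fall into the gap between them. They are not exempt as adverse events, yet they are removed from the one endpoint that counts re-operations.

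The stake is what a low SSI rate can be taken to mean. Safety and rotational stability are stated objectives, and this is a toric lens, so a return to surgery to exchange or turn the optic is a result that a reader will look for. If the SSI line reads 0/17 and nothing beside it counts exchanges and rotations, a reader cannot tell whether no eye went back to surgery or whether some did by a route that the definition removes.

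**Working it through.** The documents state no SSI rate, threshold or power, so there is no planned figure to reproduce. The main check is textual.

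**Step 1. Sort the cases by the two rules.**

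| Re-operation | Exempt from AE reporting (protocol 6.1.1)? | In the SSI rate (SAP 5.4)? |
|---|---|---|
| Optic exchange or rotation to refine refraction | Yes | No |
| Optic exchange or rotation for damage, dislocation or another device reason | No | No |
| Any other device-related re-operation | No | Yes |

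The second row is the mismatch. Protocol 6.1.4 treats damage to the device as a deficiency, and protocol 6.2 lists lens dislocation and explantation for optic damage as examples of device effects. The documents therefore regard such triggers as device problems, but the procedure that follows is not counted.

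**Step 2. Look for a count elsewhere.** The visible SAP safety outputs are BCDVA, Annex B adverse event rates, the restricted SSI rate and device deficiencies (5.4, 5.5). The visible effectiveness outputs are residual cylinder, prediction error, acuity, misalignment, rotation angle and cylinder reduction (5.7, 5.8). None tabulates concomitant procedures, which is where exchanges and rotations are recorded. The rotation and misalignment outputs report angles, not operations. SAP 5.5 does not repeat the exclusion, but it summarises the endpoints listed in 5.4, so the exclusion is read as applying.

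**Step 3. Look at the recording rule.** Protocol 4.8.2 wants the indication for each procedure in the Ocular History or AE form, with PCO as the only exception. Protocol 6.1.1 says that a refractive exchange or rotation is not an AE. Refractive error that first appears after surgery does not sit naturally in ocular history, so the reason has no clear home.

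**Step 4. Illustrate the size.** Inputs: n = 17 eyes (SAP section 6) and p = 6.7% (protocol 1.0, another toric lens, taken here as an assumption). Other values of p are assumed to show a range. Eyes are treated as independent.

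- Expected excluded events = n × p = 17 × 0.067 = 1.14.
- P(at least one) = 1 − (1 − p)^17 = 1 − 0.933^17 = 69.2%.
- At assumed p = 2%: 29.1%. At 5%: 58.2%. At 10%: 83.3%.
- One eye = 1/17 = 5.9% (exact 95% interval 0.1% to 28.7%). Two eyes = 2/17 = 11.8% (1.5% to 36.4%).

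In each of these cases the SSI line would still read 0/17 if no other device-related SSI occurred. The upper 95% limit for 0/17 is 1 − 0.05^(1/17) = 16.2% one-sided, or 1 − 0.025^(1/17) = 19.5% two-sided. That limit applies only to the restricted definition, not to all re-operations.

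**The case against.** **Disclosed design choice.** The exclusion appears consistently in the synopsis, protocol 7.1 and SAP 5.4, and 6.1.1 explains it. This stands. A reader might infer that re-operations are being concealed; the documents do not support that. The defect is a boundary wider than its stated rationale, together with a missing count.

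**Device failures surface elsewhere.** Damage is a device deficiency, which is a safety endpoint of its own. Dislocation and explantation for damage are listed device effects, and protocol 6.3.1 requires expedited reporting of explants, device effects and deficiencies. This stands for the triggering event. It does not supply a count of the exchange or rotation.

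**Rotation is measured directly.** The schedule has a reading center assess it at surgery and at every postoperative visit, and SAP 5.8.4 and 5.8.5 report misalignment and rotation. Protocol 3.3.3 also keeps the refraction from before any secondary surgery as the final result. So a poor result can still show, and it would be wrong to infer that rotational failure is hidden. These outputs still do not say that an eye was re-operated.

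**The 6.7% figure is background.** It describes another lens, no passage sets it as a comparator, and the study is descriptive. This stands, and the figure is used here only as an illustration. A reader might also apply the introduction's figure of up to 16%. That figure refers to patients having any additional surgical correction, so those procedures would not all fall under the exclusion; it is not used here.

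**Protocol 4.8.2 and 6.1.1 are not a strict contradiction.** The first concerns where the indication is listed, the second whether the procedure is an AE, and a site might enter pre-existing astigmatism as ocular history. This stands: the passages are awkward together and need reconciling, but it is too strong to say that a site cannot comply with both.

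**Missing text.** Both documents are heavily redacted, SAP numbering goes from 5.5 to 5.7, and Annex B is not reproduced. A separate count may exist there. This limits the claim of no count. It does not touch the mismatch between the SSI exclusion and 6.1.1, which rests on unredacted wording.

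**Conclusion.** The concern holds as a definition mismatch with a reporting gap. The SSI rate leaves out optic exchange and rotation for any reason, including device reasons that 6.1.1 does not exempt, and no visible output counts these procedures. A reported 0/17 would therefore not show that no lens was re-operated.

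The size depends on an unknown re-operation rate. Under the assumptions above, the chance that at least one of 17 eyes has an uncounted exchange or rotation is 69% at 6.7%, and 29% to 83% at 2% to 10%. Both eyes of a subject may be enrolled; positive correlation between them would lower these probabilities without changing the expected count. The mismatch itself needs no assumption about rates. The absence of a count is a statement about the visible text only.

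**What to change.** 1. In SAP 5.4 and 5.5, limit the SSI exclusion to exchange or rotation done solely to refine refraction, matching protocol 6.1.1. Count those done for other device-related reasons as SSIs. This keeps the sponsor's distinction for designed use.
2. Add one row to the safety table, in the Safety Population: number and percentage of eyes with any optic exchange or rotational adjustment by 3 months, by reason, taken from the Concomitant Procedure eCRF.
3. Reconcile protocol 4.8.2 with 6.1.1 so that the reason for a refractive exchange or rotation has a clear place to be recorded.

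The cost is SAP wording, one table row and one form-completion instruction; the procedures are already captured. The SAP describes enrolment as past, so item 3 may come too late for data entry. In that case the reasons can be sought from source documents, and the change can be described under the SAP's own section on deviations. The downside is that the reported re-intervention figure may look less favourable.
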